## 4.5.2 Other Restrictions and Precautions

Treatment breaks must be resumed  $\leq$  6 weeks from the last dose or the participant must be permanently discontinued from the study. (See exceptions in Sections 4.6 and 6.5.3)

Non-target bone lesions that do not include lung tissue in the planned radiation field may receive palliative radiotherapy at any time while on study treatment. Radiotherapy to non-bone lesions is permitted only as described in Section 4.5.2, but must not be given during or 2 weeks after study therapy. Details of palliative radiotherapy should be documented in the source records and case report form (CRF). Details in the source records should include: dates of treatment, anatomical site, dose administered and fractionation schedule, and AEs.

Participants requiring palliative radiotherapy should be carefully assessed for disease progression. Participants considered to have progressive disease are required to discontinue study participation, unless eligible to continue treatment beyond progression per the guidance in Section 6.5.5 (Treatment Beyond Disease Progression).

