Participants will be evaluated for response according to RECIST 1.1 criteria. Radiographic assessments will be obtained according to the study calendar schedule for the first 33 weeks and subsequently every 12 weeks, or more frequently as clinically indicated, until disease progression (or until discontinuation of study drug(s) in patients treated beyond progression) or withdrawal of study consent.

The treatment phase ends when the participant is discontinued from study drug(s)

Study assessments while on treatment are to be collected as outlined in Tables 7.1-1, 7.1-2, and 7.1-3.

**3. Follow-up.** Follow-up begins when the decision to discontinue a participant from study therapy is made.

Participants who discontinue study therapy for reasons other than disease progression will continue to have radiographic assessments according to the study calendar( $\pm 5$  days)for the first 33 weeks, and subsequently every 12 weeks, until disease progression or withdrawal of study consent.

Follow-up visits occur as follows:

- X01 Follow-up Visit 1 = 35 days  $\pm$  7 days from last dose;
- X02 Follow-up Visit 2 = 80 days  $\pm$  7 days from X01 Follow-up Visit 1;
- Survival Follow-Up visits begin after the X02 Follow-up Visit 2.

For Survival Follow-up Visits, contact of participants will occur (in person or by telephone) every 12 weeks upon entry into this phase to evaluate OS and collect data on the initiation of subsequent therapy for the treatment of SCLC.

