## **4.6 Discontinuation of Participants Following Any Treatment with Thoracic Radiation Therapy or Study Drug(s)**

Participants MUST discontinue investigational product (and non-investigational product at the discretion of the investigator) for any of the following reasons:

- Disease progression as assessed by RECIST 1.1 criteria, unless the participant meets criteria for treatment beyond progression (Section 6.5.5)
- Participant requests to stop study treatment
- Any clinical adverse event (AE), laboratory abnormality, or intercurrent illness that, in the opinion of the investigator, indicates that continued participation in the study is not in the best interest of the participant
- Discontinuation of study support by Bristol-Myers Squibb (BMS)
- Loss of ability to freely provide consent through imprisonment or involuntarily incarceration for treatment of either a psychiatric or physical (e.g., infectious disease) illness
- Additional protocol-specified reasons for discontinuation, as described in Section 6.5.3.4

In the case of pregnancy, the investigator must immediately notify the primary investigator or designee of this event. In most cases, study drug(s) will be permanently discontinued in an appropriate manner. If the investigator determines a possible favorable benefit/risk ratio that warrants continuation of study drug(s), a discussion between the primary investigator or designee, the IRB, and the Sponsor or designee must occur. All participants who discontinue study drug(s) should comply with protocol specified follow-up procedures as outlined in Section 7. The only exception to this requirement is when a participant withdraws consent for all study procedures including post-treatment study follow-up or loses the ability to consent freely (ie, is imprisoned or involuntarily incarcerated for the treatment of either a psychiatric or physical illness).

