## **4.7 Post-Study Drug Study Follow-up**

In this study, overall survival is a key endpoint of the study. Post-study follow-up is of critical importance and is essential to preserving participant safety and the integrity of the study. Participants who discontinue study drug must continue to be followed for collection of outcome and/or survival follow-up data as required and in line with Section 7 until death or the conclusion of the study. The primary investigator may request that survival data be collected on all participants outside of the protocol-defined window (see Table 7.1-5). At the time of this request, each participant will be contacted to determine their survival status unless the participant has withdrawn consent for all contact.

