### **6.5.3.3 Criteria to Resume Treatment**

Participants may resume treatment with study therapy when the drug-related AE(s) resolve to Grade  $\leq 1$  or baseline value, with the following exceptions:

- Participants may resume treatment in the presence of Grade 2 fatigue
- Participants with baseline Grade 1 AST/ALT or total bilirubin who require dose delays for reasons other than a 2-grade shift in AST/ALT or total bilirubin may resume treatment in the presence of Grade 2 AST/ALT OR total bilirubin
- Drug-related pulmonary toxicity must have resolved to baseline before treatment is resumed
- Drug-related endocrinopathies adequately controlled with only physiologic hormone replacement may resume treatment

If the criteria to resume treatment are met, the participant should restart treatment at the next scheduled timepoint per protocol. Doses should not be skipped.

If treatment is delayed  $> 6$  weeks (42 days) from the last dose due to drug-related toxicity, the participant must be permanently discontinued from study therapy, except as specified in Section 6.5.3.4. In the event treatment is

delayed > 6 weeks due to reasons other than study drug-related toxicity, the case should be discussed with the Principal Investigator before proceeding.

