#### **6.5.3.4 Discontinuation Criteria**

Treatment with study therapy should be permanently discontinued for the following:

- Any Grade 2 drug-related uveitis or eye pain or blurred vision that does not respond to topical therapy and does not improve to Grade 1 severity within the re-treatment period OR requires systemic treatment
- Any Grade 3 non-skin, drug-related AE lasting > 7 days, with the following exceptions:
  - Grade 3 drug-related uveitis, pneumonitis, bronchospasm, neurologic toxicity, hypersensitivity reaction, or infusion reaction of any duration requires discontinuation
  - Grade 3 drug-related laboratory abnormalities do not require treatment discontinuation except:
    - ◆ Grade 3 drug-related thrombocytopenia > 7 days or associated with bleeding requires discontinuation
    - ◆ Any drug-related liver function test (LFT) abnormality that meets the following criteria require discontinuation:
      - AST or ALT > 8 x ULN
      - Total bilirubin > 5 x ULN
      - Concurrent AST or ALT > 3 x ULN and total bilirubin > 2 x ULN
- Any Grade 4 drug-related AE or laboratory abnormality, except for the following events which do not require discontinuation:
  - Grade 4 neutropenia  $\leq$  7 days
  - Grade 4 lymphopenia or leukopenia
  - Isolated Grade 4 electrolyte imbalances/abnormalities that are not associated with clinical sequelae and are corrected with supplementation/appropriate management within 72 hours of their onset
  - Grade 4 amylase or lipase abnormalities that are not associated with symptoms or clinical manifestations, or radiographic signs of pancreatitis. It is recommended to consult with the Principal Investigator for Grade 4 amylase or lipase abnormalities
  - For Grade 4 endocrinopathy AEs such as adrenal insufficiency, ACTH deficiency, hyper or hypothyroidosis, or glucose intolerance, which resolve or are adequately controlled with physiologic hormone replacement (steroids, thyroid hormones) or glucose controlling agents, respectively, retreatment can be considered after discussion with the Principal Investigator
- Any dosing interruption lasting > 6 weeks from the last dose with the following exceptions:

- Dosing interruptions to allow for prolonged steroid tapers to manage drug-related AEs are allowed. Prior to re-initiating treatment in a participant with a dosing interruption lasting > 6 weeks from the last dose, the Principal Investigator must be consulted

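### Two phrases in Section 4.5.2 take patients off the study where other sections stop study therapy only and require follow-up; followed literally, they would cost 6-month PFS status and survival data.

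*Combined protocol and SAP*

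**What the plan says.** Section 4.5.2 (Other Restrictions and Precautions) contains two removal rules.

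- **Long break.** Treatment must resume within "6 weeks from the last dose or the participant must be permanently discontinued from the study". The sentence points to exceptions in Sections 4.6 and 6.5.3.
- **Progression.** In the paragraph on patients who need palliative radiotherapy: "Participants considered to have progressive disease are required to discontinue study participation, unless eligible to continue treatment beyond progression".

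Other sections end treatment, not participation, for the same triggers.

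- Section 6.5.3.3, delay over 6 weeks for drug-related toxicity: "the participant must be permanently discontinued from study therapy, except as specified in Section 6.5.3.4".
- Section 6.5.3.4, whose list includes an interruption over 6 weeks: "Treatment with study therapy should be permanently discontinued for the following".
- Section 4.6, whose list includes RECIST progression, stops the investigational product.

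Follow-up then continues.

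- Section 4.2.1: "Participants who discontinue study therapy for reasons other than disease progression will continue to have radiographic assessments", followed by survival contact every 12 weeks.
- Section 4.6: "All participants who discontinue study drug(s) should comply with protocol specified follow-up procedures as outlined in Section 7". There are two exceptions: withdrawal of consent for all study procedures including follow-up, and loss of the ability to consent freely.
- Section 4.7: "Participants who discontinue study drug must continue to be followed for collection of outcome and/or survival follow-up data", until death or the end of the study.
- Section 4.7.1 states that a patient who asks to stop therapy stays on the study.
- Section 7.4.1 seeks survival and imaging data on everyone, including those withdrawn from treatment.

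**The concern.** Section 4.7.1 separates stopping therapy from leaving the study. Against that usage, the two phrases in 4.5.2 read as leaving it. The trial is multicentre, with up to five sites besides the lead, so each site could settle the conflict in its own way.

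The two rules put different data at risk. A patient removed for a long break without progression loses later scans and survival contact. Under 9.4.1 that patient is censored for PFS at the last disease assessment, and under 9.4.2 for OS at the last contact. A patient removed at documented progression already has a PFS event, so mainly OS is lost.

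Removal follows toxicity delay or progression, so the censoring is not independent of outcome. The decision rule in 9.2 needs each patient's status at 6 months, and no section says how a patient with unknown status is counted.

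**Working it through.** **1. Does the pointer in 4.5.2 resolve the conflict?** It does not. The exceptions in 6.5.3 concern who may resume dosing after a long interruption. The exceptions in 4.6 release patients from follow-up. Neither keeps in follow-up a patient who has been taken off the study. The progression sentence has one exception only, treatment beyond progression.

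**2. The plan's own design.** Inputs from 9.2: null 24%, alternative 44%, first stage 18 patients (stop at 4 or fewer progression-free), total 52, reject at 18 or more. The probability of rejection is

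sum over x = 5 to 18 of Bin(x; 18, p) × P[Bin(34, p) ≥ 18 − x].

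At p = 0.24 this is 0.0494, and at p = 0.44 it is 0.9035. The stated 0.05 and 90% reproduce when every 6-month status is known.

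**3. Break rule and PFS.** The documents do not give the number of patients who would be removed, so the shares q of 5%, 10% and 20% are assumptions.

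- (a) If a share q of patients who would be progression-free at 6 months is removed and counted as failures, p becomes 0.44 × (1 − q) = 0.418, 0.396 or 0.352. Power falls from 0.90 to 0.85, 0.77 or 0.54.
- (b) If instead a share q of the PFS hazard is censored rather than observed, the Kaplan-Meier value tends to S^(1 − q). A true 24% reads as 25.8%, 27.7% or 31.9%. A true 44% reads as 45.8%, 47.8% or 51.9%.

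The direction therefore depends on how lost patients are handled: (a) works against the regimen, and (b), under the Kaplan-Meier analysis in 9.5.2, favours it.

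**4. Progression rule and OS.** Assumptions, none from the documents except the two PFS rates: exponential times, 10% of PFS events are direct deaths, median time from progression to death (m) of 4 to 8 months, and a share q of progressing patients censored at progression. With λ = −ln(6-month PFS)/6 and μ = ln 2/m:

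- alive without progression: A(t) = exp(−λt)
- alive after progression: B(t) = 0.9λ[exp(−μt) − exp(−λt)]/(λ − μ)
- hazard seen by Kaplan-Meier: h(t) = [0.1λA + μ(1 − q)B]/[A + (1 − q)B]
- estimated 12-month OS: exp(−integral of h from 0 to 12)

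| 6-month PFS | m (months) | True 12-month OS | q = 10% | q = 30% |
|---|---|---|---|---|
| 24% | 4 | 28.1% | 29.2% | 32.1% |
| 24% | 6 | 39.4% | 40.3% | 42.6% |
| 24% | 8 | 47.7% | 48.4% | 50.1% |
| 44% | 4 | 42.5% | 44.3% | 48.8% |

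Across these rows the upward bias is 0.7 to 1.8 points at q = 10% and 2.5 to 6.2 points at q = 30% (differences taken before rounding). For scale, the approximate 95% half-width for an OS rate near 42% with 52 patients is 1.96 × √(0.424 × 0.576/52) = 0.134, about 13 points.

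**The case against.** The strongest reply is that the rest of the protocol already settles the matter. Sections 4.2.1, 4.6, 4.7, 4.7.1 and 7.4.1 require follow-up. Sections 6.5.3.4 and 7.4 continue tumour assessments when dosing is interrupted or delayed. Table 7.1-5 ends survival visits only at death, loss to follow-up or withdrawal of consent. The protocol also uses study discontinuation loosely: Table 7.5-1 and Section 8.4 use that term while follow-up still takes place. In 4.5.2 itself, the alternative to ending participation is continuing treatment. Section 4.5.2 concerns concomitant treatment, not follow-up. The break rule is narrowed by the exceptions in 6.5.3.4, and 9.2 allows up to 10% more patients for censoring.

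Most of this stands. It makes therapy-only the likely intent and limits how many sites would act otherwise. It does not remove the conflict, because the two phrases remain in force and the cited exceptions do not address follow-up.

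A reader might infer that every patient leaves at progression and that OS is heavily overstated. The documents do not support that: the sentence sits in the palliative-radiotherapy paragraph and plausibly reaches only those patients. Nor does removal at a documented progression cost PFS data. PFS would be lost there only if the judged progression was never recorded as such.

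**Conclusion.** The contradiction is real and rests on the text alone. Section 4.5.2 is the outlier, and the likely intent is to stop therapy only. The harm is conditional on a site following 4.5.2 literally: 6-month PFS status would be lost after long breaks, and survival data would be lost in both groups, through informative censoring.

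The size cannot be derived from the documents. Under the stated assumptions the OS bias is about 1 to 2 points at 12 months if 10% of progressing patients are removed, which is small beside the sampling error. The PFS figures show only how sensitive the design is to lost status; they do not forecast how many patients would be lost. This is a wording inconsistency to correct, not a flaw in the design.

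**What to change.** Reconcile 4.5.2 with the sections above by replacing both phrases with: *discontinued from study therapy; follow-up continues per 4.2.1, 4.6 and 4.7*. Make clear that scans run to progression, with survival contact thereafter, as already planned. Keep both exceptions in 4.6: withdrawal of consent for all study procedures including follow-up, and loss of the ability to consent freely. A statement that only withdrawal of consent for contact ends data collection would conflict with the second exception and with the planned end of scans at progression.

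Leave the 6-week limit and the clinical criteria for stopping therapy unchanged. No design figure changes: with complete status, N = 52, alpha 0.0494 and power 0.9035. The cost is two phrases in an amendment and a notice to sites, since the scans and survival contacts are already scheduled.

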### ***Imaging Restrictions and Precautions***

It is the local imaging facility's responsibility to determine, based on patient attributes (e.g., allergy history, diabetic history, and renal status), the appropriate imaging modality and contrast regimen for each participant. Imaging contraindications and contrast risks should be considered in this assessment. Participants with renal insufficiency should be assessed as to whether they should receive contrast and, if so, what type and dose of contrast is appropriate. Specific to MRI, patients with severe renal insufficiency (i.e., estimated glomerular filtration rate (eGFR)  $< 30$  mL/min/1.73m^2) are at increased risk of nephrogenic systemic fibrosis. MRI contrast should not be given to this population. In addition, participants are excluded from MRI if they have tattoos, metallic implants, pacemakers, etc. The ultimate decision to perform MRI in an individual in this study rests with the site radiologist, the investigator, and the standard set by the local Ethics Committee.

## 4.5.3 Permitted Therapy

Participants are permitted to use topical, ocular, intra-articular, intranasal, and inhalational corticosteroids (with minimal systemic absorption). Adrenal replacement steroid doses including doses  $> 10$  mg daily prednisone are permitted. A brief (less than 3 weeks) course of corticosteroids for prophylaxis (e.g., contrast dye allergy) or for treatment of non-autoimmune conditions (e.g., delayed-type hypersensitivity reaction caused by a contact

allergen) is permitted. Postmenopausal women may continue HRT after FSH testing is completed and postmenopausal status is confirmed. Concomitant palliative and supportive care for disease-related symptoms (including bisphosphonates and RANK-L inhibitors) are allowed. See Section 4.5.2 for guidance on concomitant palliative radiotherapy. Caution should be used regarding the use of herbal medications as there may be as yet unknown interactions with study therapy. Discontinuation of the use of herbal medications prior to study initiation is encouraged.

## **4.6 Discontinuation of Participants Following Any Treatment with Thoracic Radiation Therapy or Study Drug(s)**

Participants MUST discontinue investigational product (and non-investigational product at the discretion of the investigator) for any of the following reasons:

- Disease progression as assessed by RECIST 1.1 criteria, unless the participant meets criteria for treatment beyond progression (Section 6.5.5)
- Participant requests to stop study treatment
- Any clinical adverse event (AE), laboratory abnormality, or intercurrent illness that, in the opinion of the investigator, indicates that continued participation in the study is not in the best interest of the participant
- Discontinuation of study support by Bristol-Myers Squibb (BMS)
- Loss of ability to freely provide consent through imprisonment or involuntarily incarceration for treatment of either a psychiatric or physical (e.g., infectious disease) illness
- Additional protocol-specified reasons for discontinuation, as described in Section 6.5.3.4

In the case of pregnancy, the investigator must immediately notify the primary investigator or designee of this event. In most cases, study drug(s) will be permanently discontinued in an appropriate manner. If the investigator determines a possible favorable benefit/risk ratio that warrants continuation of study drug(s), a discussion between the primary investigator or designee, the IRB, and the Sponsor or designee must occur. All participants who discontinue study drug(s) should comply with protocol specified follow-up procedures as outlined in Section 7. The only exception to this requirement is when a participant withdraws consent for all study procedures including post-treatment study follow-up or loses the ability to consent freely (ie, is imprisoned or involuntarily incarcerated for the treatment of either a psychiatric or physical illness).

Participants must be followed for at least 100 days after the last dose of study therapy. Follow-up visit 1 (FU1) occurs approximately 35 days (+/- 7 days) after last dose of coinciding with the date of discontinuation (+/- 7 days) if the date of discontinuation is greater than 35 days after the last dose. Follow-up visit 2 (FU2) occurs approximately 80 days (+/- 7 days) after FU1. Survival visits are every 3 months from FU2 up to 5 years and may be conducted during a clinic visit or via the phone. The primary endpoint of this study is PFS with a secondary endpoint of OS so tracking reporting the participant's status in the follow-up setting according to the protocol guidelines for disease progression and survival are critical to the final study analysis. The importance of follow-up should be clearly communicated to study participants. If the study drug(s) is discontinued prior to

the patient completion of the study, the reason for the discontinuation must be documented in the patient's medical records and entered on the appropriate case report form (CRF) page.

## **4.7 Post-Study Drug Study Follow-up**

In this study, overall survival is a key endpoint of the study. Post-study follow-up is of critical importance and is essential to preserving participant safety and the integrity of the study. Participants who discontinue study drug must continue to be followed for collection of outcome and/or survival follow-up data as required and in line with Section 7 until death or the conclusion of the study. The primary investigator may request that survival data be collected on all participants outside of the protocol-defined window (see Table 7.1-5). At the time of this request, each participant will be contacted to determine their survival status unless the participant has withdrawn consent for all contact.

### **4.7.1 Withdrawal of Consent**

Participants who request to discontinue study therapy will remain on the study and must continue to be followed for protocol-specified follow-up procedures. The only exception to this is when a participant specifically withdraws consent for any further contact with him/her or persons previously authorized by the participant to provide this information. Participants should notify the investigator of the decision to withdraw consent from future follow-up in writing, if possible. The withdrawal of consent should be explained in detail in the medical records by the investigator, as to whether the withdrawal is from further treatment with study therapy only or also from study procedures and/or post-treatment study follow-up, and entered on the appropriate CRF page. In the event that vital status (whether the participant is alive or dead) is being measured, publicly available information should be used to determine vital status only as appropriately directed in accordance with local law.

